1. INTRODUCTION AND OBJECTIVES OF ANALYSIS

1.1. Introduction

This document presents the statistical analysis plan (SAP) addendum for Arrowhead Pharmaceuticals, Protocol AROAAT2001: A Placebo-Controlled, Multi-dose, Phase 2 Study to Determine the Safety, Tolerability and Pharmacodynamic Effect of Fazirsiran in Patients with Alpha-1 Antitrypsin Deficiency (AATD) [SEQUOIA].

This SAP Addendum is based on the AROAAT2001, V6.0, protocol dated 29 August 2022. Per the final SAPv3.0 signed prior to study unblinding, "Data collected in an open label stage will be descriptively summarized". The purpose of this SAP Addendum is to provide further detail on these open-label phase descriptive statistics. Analyses that were described in the final SAPv3.0 will not be described again in this document.

The formats for the tables, figures, and listings (TFLs) described in this SAP are provided in a companion document. A table of contents for the TFLs will be included in the companion document.

1.2. Objectives and Endpoints

Refer to SAPv3.0.

2. STUDY DESIGN

Refer to SAPv3.0.

3. SUBJECT POPULATIONS

Refer to SAPv3.0.

3.1. Population Definitions

The following population samples for analyses will be evaluated and used for presentation and analysis of data captured during the open-label phase:

• Open-label Phase Set: All subjects who receive at least one dose of Fazirsiran in the open-label phase.

4. DEFINITIONS AND DATA HANDLING

The following general data handling conventions, will be used in the derivation of variables used in summaries of the open-label phase data:

Term	Definition/Rule	
Baseline	The latest measurement performed prior to the first dose of open-label phase Fazirsiran.	
Study Day	(Date of assessment) – (date of first dose of open-label phase Fazirsiran) + 1, if date of	
	assessment \geq date of first dose of open-label phase Fazirsiran;	
	(Date of assessment) – (date of first dose of open-label phase Fazirsiran), if date of	
	assessment < date of first dose of open-label phase Fazirsiran	
TEAE	Adverse event that first occurred or worsened in severity following dose administration of	
	the first dose of open-label phase Fazirsiran through EOS or Early Termination	
TESAE	Serious adverse event that first occurred or worsened in severity following dose	
	administration of the first dose of open-label phase Fazirsiran through EOS or Early	
	Termination	

Table 1: Definitions

For other general definitions and data handling, refer to SAPv3.0.

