Unless otherwise noted, baseline values will be those assessments obtained pre-dose within the closest proximity to the first dose.

Safety Assessments will be performed at specified timepoints per the SOA and will include the following:

- Vital signs: Resting HR, seated or semi-supine (same position each time is preferred) systolic/diastolic BP, RR, and temperature
- Clinical laboratory measurements (e.g., biochemistry, hematology, cardiac troponin, lipids, coagulation, FSH, urine pregnancy test [women of childbearing potential {WOCBP}], urine cotinine, and urinalysis)
- Resting ECG measurements (measured after patient is supine or semi-supine [same position each time is preferred] for at least 3 minutes)
- At each visit, patients will be asked about concomitant medications/therapy and will be instructed to volunteer any information regarding AEs and serious adverse events (SAEs) that they may have experienced. Any known untoward event that occurs beyond the AE reporting period that the Investigator(s) considers an SAE and possibly related to study treatment will be reported to the Sponsor

- 90-day, post-last dose follow-up phone call to assess for pregnancy occurrence
- Physical examination (symptom directed as described in the SOA)
- Pulmonary Function Testing including spirometry (including VC, FVC, FEV₁, FEV₁/VC, and FEV₁/FVC) and DLCO
- Use of augmentation treatment at any time throughout the study
- Time from baseline to initiation of augmentation therapy
- Number and severity of chronic obstructive pulmonary disease (COPD)
 exacerbations based on Global Initiative for Chronic Obstructive Lung Disease
 (GOLD) criteria in active versus placebo will be evaluated as an AE of special
 interest

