targeting AAT indicate that PiZZ patients respond to hepatocyte targeted siRNA silencing of AAT in a manner similar to healthy volunteers at equivalent dose levels (Turner et al., 2018). Finally, although similar serum AAT reduction, following multiple doses of 100 and 200 mg, were observed, there is less inter-subject variability in serum AAT reduction at the higher dose level and an apparent longer duration of effect. It is possible that 200 mg will produce greater suppression in liver Z-AAT production than the 100 mg dose. Arrowhead believes the greater the suppression of liver Z-AAT protein production, the greater potential for improvement in disease. This is based on other liver diseases such as HBV/HCV, where full or near full removal of the insulting agent has been observed to allow the liver to begin the regenerative process.

The rationale for the proposed dosing interval is based on the goal of targeting AATD patients exhibiting liver fibrosis with the aim of halting the liver insult and damage produced by polymerized aggregates of Z-AAT as early and effectively as possible. Providing a dose on Day 1 followed by a dose on Day 29 (Week 4) is likely to more rapidly drive hepatic AAT levels to maximally reduced levels (similar to a loading dose strategy) followed by a maintenance dose 12 weeks after the second dose on Day 113 (Week 16) and dosing approximately quarterly thereafter. This strategy of maximizing ablation of liver AAT early should yield the most benefit to patients in terms of liver PiZ protein reduction over the course of the study, while then moving to quarterly dosing should maximize safety by limiting patient exposure to drug. The administration of the third fazirsiran dose (and subsequent doses later in development) at Day 113 (Week 16) and quarterly dosing thereafter is based on AROAAT1001 single dose data showing duration of PD activity with rebound in serum AAT levels beginning approximately 12 weeks after dose administration. Approximate quarterly dosing should minimize additional unnecessary dosing and minimize safety risk.

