5.3. Secondary Endpoints

- Subject incidence of treatment-emergent AEs
- Absolute and percent change from baseline in total liver Z-AAT (insoluble + soluble) protein at post-dose biopsy visit
- Absolute and percent change from baseline in liver Z-AAT soluble protein at post-dose biopsy visit
- Absolute and percent change from baseline in liver Z-AAT insoluble protein at post-dose biopsy visit
- Absolute and percent change from baseline in liver function tests including ALT, aspartate aminotransferase (AST), alkaline phosphatase (ALP), gamma glutamyl transferase (GGT), total bilirubin, direct bilirubin, and international normalized ratio (INR) at Week 16 and over time through End of Study (EOS)
- Absolute and percent change in serum Z-AAT over time through EOS
- Change over time in PK measurements of fazirsiran at timepoints specified in the Schedule of Assessments (SOA)
- Incidence of anti-drug antibodies (ADAs) to fazirsiran
- Change from baseline in Metavir fibrosis stage at post-dose biopsy

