9.3.8. Pharmacodynamics

Serum Alpha-1 Antitrypsin Level: Serum levels of alpha-1 antitrypsin will be obtained at Screening and on Day 1 prior to dose administration. Z-AAT serum levels will also be measured as per SOA. The Day 1 value will be used as each patient's baseline value for data analysis purposes. Serum alpha-1 antitrypsin levels will be measured as per the SOA. Samples will be analyzed by standard clinical laboratory assay for serum alpha-1 antitrypsin levels and Z-AAT levels using a Z-specific assay. Z-AAT values will be used for final analysis.

Liver Biopsy: Pre-dose (Screening) and post-dose (per the SOA) percutaneous liver biopsies will be conducted to obtain tissue samples for liver Z-AAT levels and histological evaluation. Per core sample, approximately 30 mm of tissue will be obtained containing at least 11 portal tracts using a 16-gauge needle. Procedure detail and tissue processing protocols are outlined in the Laboratory Manual. Left over tissue samples may be retained and stored for possible future additional analysis. Any retained samples will be deidentified and will not be labeled with patient identifying information. After 10 years from the end of the study, samples will be returned to the primary Institution or local repository or destroyed per local regulations. Tissue samples will be utilized for the following evaluations:

- Soluble liver AAT protein levels
- Insoluble liver AAT protein levels
- Fibrosis gene expression
- SERPINA1 mRNA expression
- Total (soluble plus insoluble) liver AAT protein levels
- Z-AAT protein PAS/D+ globules (globule size and number)
- Metavir fibrosis stage
- Liver histological evaluation
- Iron content using biomarkers, special stains, and imaging (Masson's Trichrome, Sirius Red, Iron, PAS-D, if scientifically feasible and sufficient sample available)

Two liver biopsy passes will be made to obtain 2 core samples each consisting of approximately 30 mm of tissue. In the event that only one core can be obtained, it should be used for histologic analysis. Additional details around performing biopsy and sample processing/logistics are present in a separate Laboratory Manual.

Serum Fibrosis Markers:

PRO-C3 and PRO-C6 will be measured as a serum marker of liver fibrosis per SOA. Biomarkers of liver disease such as APRI and FIB-4 will be calculated using ALT, AST, age variables.

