6.3. Pharmacodynamic Evaluations

Serum Z-AAT value and derived change/percent change from baseline at each open-label visit will be summarized.

Serum Fibrosis Markers

A descriptive statistics summary of serum Pro-C3, Pro-C6, APRI and FIB-4 by open-label visit will be provided by fibrosis status at Screening. Derived changes from baseline and percent changes from baseline will be included. Subgroup analysis based on central read Metavir score will be done.

FIB-4: FIB-4 is calculated as

 $FIB4 = (Age (yr) * AST(U/L))/(Platelet Count(10^9/L) * \sqrt{(ALT(U/L))})$

APRI: APRI is calculated as

 $APRI = ((AST(U/L))/(AST(upper limit of normal U/L)))/(Platelet Count(10^9/L))$

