6.4.2. Laboratory Data

Laboratory data (details refer to Protocol section 9.2.6), including biochemistry, hematology, and coagulation will be summarized using descriptive statistics at each open-label visit. For continuous parameters, a summary of the change from baseline and percent change from baseline to each post dose laboratory assessment in the open-label phase will be produced. Shifts in selected laboratory parameters between baseline and the worst open-label assessment value will be summarized according NCI CTCAE toxicity grades. The number and percent of subjects will be reported in each shift category.

Separate summary table will be generated for ALT, AST, alkaline phosphatase, CK, GGT, total bilirubin, direct bilirubin and INR. An evaluation of drug-induced serious hepatotoxicity (eDISH) scatter plot will be produced for the open-label phase. Maximum total bilirubin (presented as xULN) will be plotted on a log scale on the y-axis and maximum ALT (presented as xULN) will be plotted on a log scale on the x-axis. A horizontal reference line will be placed at 2x ULN for maximum total bilirubin, and a vertical reference line will be placed at 3x ULN for maximum ALT. The lower left quadrant will be labeled "Normal Range". The upper left quadrant will be labeled "Cholestasis Quadrant". The lower right quadrant will be labeled "Temple's Corollary Quadrant". The upper right quadrant will be labeled "Hy's Law Quadrant".

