6.4.6. Pulmonary Function

Refer to SAPv3.0 for additional details related to pulmonary function assessments.

Change from baseline in pulmonary function test parameters (PFT) will be summarized by time point for openlabel phase visits. Additional plots of PFT parameters and change from baseline trend will be generated.

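### In the SAP addendum, all open-label change is measured from the last value before open-label dosing, a reference that is on-drug for former active patients and unexposed for former placebo patients, with no companion change from Day 1 and no split by prior arm

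*SAP*

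**What the plan says.** The SAP addendum, section 4, sets the conventions for variables in the open-label summaries. Baseline there is "The latest measurement performed prior to the first dose of open-label phase Fazirsiran". Later sections of the addendum use it:

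- Section 6.3: "Serum Z-AAT value and derived change/percent change from baseline at each open-label visit will be summarized". PRO-C3, PRO-C6, APRI and FIB-4 are handled the same way.
- Section 6.4.2: change and percent change in laboratory values, and "Shifts in selected laboratory parameters between baseline and the worst open-label assessment value will be summarized".
- Section 6.4.6: "Change from baseline in pulmonary function test parameters (PFT) will be summarized by time point for openlabel phase visits".

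The protocol's references are different. The synopsis gives a general rule: "Unless otherwise noted, baseline values will be those assessments obtained pre-dose within the closest proximity to the first dose". For serum AAT and Z-AAT, Protocol 9.3.8 is specific: "The Day 1 value will be used as each patient's baseline value for data analysis purposes". Section 11.10 also uses the Day 1 pre-dose value for Z-AAT. The secondary endpoints in Protocol 5.3 include "Absolute and percent change in serum Z-AAT over time through EOS", and change in liver tests through the same point. For patients with fibrosis who continue, end of study lies in the open-label phase.

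The only group splits the addendum names are fibrosis status at Screening (6.3, 6.4.1) and central-read Metavir score (6.3). Patients without fibrosis do not enter the open-label phase (Protocol 6.2), so the first split leaves essentially one group. Prior treatment is not named.

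**The concern.** Fibrosis patients from every randomised arm move to the selected open-label dose after their post-dose biopsy (Protocol 6.1). No washout is stated. A former active patient's reset baseline is therefore a treated value, and a former placebo patient's is an untreated one. Change from that baseline answers two different questions under one label.

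Two things are at stake. First, at the same level of Z-AAT suppression, former active patients would look like weaker responders than former placebo patients. Secondly, laboratory or lung-function change that former active patients built up in the double-blind phase is subtracted out of the open-label change tables, although Protocol 6.2 gives long-term safety as the purpose of that phase. The addendum defines no table that shows cumulative change from Day 1 across both phases.

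**Working it through.** The plan gives no figure of its own here, so the check is what the stated definition produces.

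**Inputs**

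- Dosing at Day 1, Week 4, Week 16, then every 12 weeks; biopsy at Week 48, 72 or 96 (Protocol 6.1).
- Duration of effect: Protocol 4.9 describes "duration of PD activity with rebound in serum AAT levels beginning approximately 12 weeks after dose administration", from single-dose data in an earlier study.
- Anticipated near-maximum serum reduction of about 90% (Protocol 4.8). Section 4.9 gives about 90% for 100 and 200 mg after multiple doses in the earlier study, and no figure for 25 mg.
- Assumed: all patients are 90% below Day 1 during open label, placebo values are flat before the switch, and knockdown at the switch in former active patients lies between 60% and 90%.

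**Step 1: state at the switch.** Doses fall at Weeks 0, 4, 16, 28, 40, 52, 64, 76, 88, 100 and so on.

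| Biopsy week | Doses before biopsy | Last dose (week) | Switch visit (week) | Gap (weeks) |
|---|---|---|---|---|
| 48 | 5 | 40 | 52 | 12 |
| 72 | 7 | 64 | 76 | 12 |
| 96 | 9 | 88 | 100 | 12 |

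Rebound is expected only to be starting at about 12 weeks, so the reset baseline of former active patients is still on-drug.

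**Step 2: Z-AAT change.** Set Day 1 = 100. The value at the switch is b = 100 - knockdown, and the open-label value is 10. Change from the reset baseline is 100 × (10 - b)/b. Change from Day 1 is 10 - 100 = -90% in every row. For former placebo patients b = 100, so they read -90% on either reference.

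| Knockdown at switch | b | Former active, reset baseline | Former placebo | Gap (points) |
|---|---|---|---|---|
| 90% | 10 | 0% | -90% | 90.0 |
| 85% | 15 | -33.3% | -90% | 56.7 |
| 80% | 20 | -50.0% | -90% | 40.0 |
| 75% | 25 | -60.0% | -90% | 30.0 |
| 70% | 30 | -66.7% | -90% | 23.3 |
| 60% | 40 | -75.0% | -90% | 15.0 |

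The true difference between the groups is zero in every row.

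**Step 3: small drifts.** A drift of one point on the Day 1 scale is multiplied by 100/b on the reset scale: 10 times at b = 10, 5 times at b = 20. From b = 10, a rise to 15 (-85% from Day 1) reads as 100 × 5/10 = +50%. A fall to 8 (-92% from Day 1) reads as -20%.

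**Step 4: time on drug before the reset.** If the last dose is at Week 196, the share of a former active patient's dosing period before the switch is 52/196 = 26.5%, 76/196 = 38.8% or 100/196 = 51.0%. If the last dose is at Week 100, a switch at Week 52 or 76 puts 52% or 76% before it. Laboratory and lung-function change over that time is not in the open-label change tables.

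**The case against.** The strongest reply is that SAPv3.0 was not among the documents. The addendum says that it does not restate analyses already there, and it refers to SAPv3.0 for endpoints, planned analyses and other definitions. Change from Day 1 through end of study may well be specified in it. That stands. A reader might infer that Day 1 has been abandoned for the whole plan, but the documents do not show this: section 4 of the addendum governs open-label summaries only, and the protocol's Day 1 rule is not withdrawn. The point remains for the addendum because section 1.1 gives it the task of detailing the open-label summaries, and quotes SAPv3.0 only as summarising that phase descriptively.

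Next, resetting baseline at a phase change is a legitimate choice. Former placebo patients start drug, and former 25 and 100 mg patients change dose. The last value before the switch is the natural reference for what happens afterwards, and it matches the open-label adverse event definition in the same table. The protocol's general rule also allows exceptions. All of this stands. It is a reason to keep the reset baseline, but not to show it alone.

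Thirdly, an apparent gap between arms appears only if the tables are split by arm, and arm labels with observed Z-AAT values would help explain it. This is partly right, but labels do not make the change figures comparable. A reader might instead infer that the arms will be pooled. That is not shown: Protocol sections 9.9.1, 11, 11.5 and 11.8 group by cohort or treatment by default, and the table shells were not supplied.

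Finally, a reader might infer that lung-function decline would go unnoticed. The documents do not support this. Sponsor review (Protocol 4.8), Appendix 3 and the DSMB work from patient data, not from these tables. Observed PFT values are plotted, double-blind change is reported separately, and adverse events are summarised for both phases. The addendum plans no separate open-label listings, which suggests that the patient listings span both phases.

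**Conclusion.** The point holds for the addendum, at minor severity. The only change it defines at open-label visits is from a reference whose meaning depends on prior arm. Under the stated assumptions, this produces a 15 to 90 point difference in Z-AAT percent change between groups with equal suppression. The width of that range reflects an unknown: the documents give no knockdown figure for these patients at the switch. The direction needs only that former active patients are still suppressed then, which the dosing interval and the stated duration of effect support, provided dosing was not interrupted earlier.

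No hypothesis test or dose decision rests on these tables. The addendum plans no separate efficacy analysis (6.2), and the Week 16 primary analysis and the biopsy comparison are untouched. The cost is to interpretation: neither Z-AAT response nor cumulative laboratory and lung-function change in former active patients can be read from the open-label change tables.

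**What to change.** Keep the open-label baseline as the reference for change after the switch. In the addendum, add change from the Day 1 pre-dose value at open-label visits for Z-AAT, liver tests, fibrosis markers and lung function, and show both references by prior active versus prior placebo. State in each table title or footnote which baseline is used. If SAPv3.0 or a table shell already provides this, a cross-reference to it in the addendum is enough.

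The cost is addendum wording and extra table rows; no new data are needed. The drawback is longer tables with small columns: if 24 patients enter at 2:1, about 24 × 2/3 = 16 former active and 24 × 1/3 = 8 former placebo.

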5. PLANNED ANALYSIS

Refer to SAPv3.0

6. STATISTICAL METHODS OF ANALYSIS

6.1. General Considerations

Refer to SAPv3.0.

As indicated in the protocol Schedule of Assessments, select assessments continue into the open-label phase. Generally, data collected in the open-label phase will by descriptively summarized in separate summaries from those pertaining to data collected in the double-blind phase.

No separate open-label phase listings will be generated.

6.2. Efficacy Evaluation

No separate efficacy analyses will be performed.

6.3. Pharmacodynamic Evaluations

Serum Z-AAT value and derived change/percent change from baseline at each open-label visit will be summarized.

Serum Fibrosis Markers

A descriptive statistics summary of serum Pro-C3, Pro-C6, APRI and FIB-4 by open-label visit will be provided by fibrosis status at Screening. Derived changes from baseline and percent changes from baseline will be included. Subgroup analysis based on central read Metavir score will be done.

FIB-4: FIB-4 is calculated as

 $FIB4 = (Age (yr) * AST(U/L))/(Platelet Count(10^9/L) * \sqrt{(ALT(U/L))})$

APRI: APRI is calculated as

 $APRI = ((AST(U/L))/(AST(upper limit of normal U/L)))/(Platelet Count(10^9/L))$

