7.3. Exclusion Criteria

A potential patient will be excluded from the study if any of the following criteria apply:

- 1. INR ≥1.2 at Screening (one retest permitted). If based on opinion of Investigator and/or prescribing physician patient is appropriate for anticoagulant holiday, patient may stop taking anticoagulant for an appropriate washout period and if indicated a repeat INR within <1.2 would be acceptable. Vitamin K may be used for reversal. If INR is not indicated (direct thrombin inhibitors or Xa inhibitors) then appropriate washout period alone may be acceptable. (Note: Anti-platelet agents, aspirin, clopidogrel or nonsteroidal anti-inflammatory drugs [NSAIDs] are acceptable but must be held 7 days before and 7 days after liver biopsy)
- 2. Platelet count $<150 \times 10^9/L$ at Screening (one retest permitted)
- 3. ALT and AST levels >250 U/L at Screening (one retest permitted)
- 4. Estimated glomerular filtration rate (eGFR) <60 mL/min/1.73m² at Screening (one retest permitted)
- 5. FEV₁ <65% of predicted (preferentially post-bronchodilatory reading) at Screening (one retest permitted)
- 6. Recent (last 3 months) pneumonia or lower respiratory infection (which must be verifiable from the medical record). Patient reported infection is not sufficient to meet this criterion.
- 7. Unavoidable exposure to inhaled environmental toxins that in the clinical judgment of the Investigator could impair pulmonary function significantly over the course of the study.

- 8. Human immunodeficiency virus (HIV) infection, as shown by the presence of anti-HIV antibody (sero-positive)
- 9. Seropositive for HBV (HBsAg positive at Screening) or HCV (detectable HCV RNA at Screening). Cured HCV (positive antibody test without detectable HCV RNA is acceptable).
- 10. Uncontrolled hypertension (Systolic BP >170 and diastolic blood pressure [BP] >100 mmHg at Screening). Patients may rescreen once BP is successfully controlled.
- 11. A history of torsades de pointes, ventricular rhythm disturbances (e.g., ventricular tachycardia or fibrillation), untreated heart block (excluding first-degree block, being PR interval prolongation only), congenital long QT syndrome or new acute ST segment elevation or depression or new acute Q wave on ECG. Stable atrial dysrhythmias (e.g., stable atrial fibrillation) are acceptable.

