If the baseline liver enzymes are normal, follow the FDA guidance on "Drug- Induced Liver Injury: Premarketing Clinical Evaluation" for monitoring and managing patients if the patients experience elevations in liver enzymes during the clinical trial.

Patients who live far from study sites may be evaluated locally for history, physical exam, and laboratories, if the results are communicated promptly to the site Investigator.

Additional laboratory criteria to detect DILI:

• Interrupt the treatment and initiate DILI evaluation if:

- O Alkaline phosphatase (ALP)>2x ULN and direct bilirubin (DB) >2x ULN, if ALP and DB are normal at baseline
- \circ ALP >2x baseline and DB >2x baseline if they are elevated at baseline
- ALP >2x baseline and DB >2x baseline and symptoms consistent with clinical hepatitis
- In the event of liver enzyme elevation, perform a DILI evaluation. If a clear etiology is established to account for the liver enzyme abnormalities, and the liver enzymes return back to baseline, the study drug may be restarted.
- If upon rechallenge, any magnitude of liver enzyme elevation recurs, the patient should cease the treatment drug and should be followed in the study. If a patient cannot be followed with laboratory or clinical monitoring, rechallenge should not be performed.

Stopping rule for progression to cirrhosis during the study:

APRI (using 40 U/L as ULN) will be calculated per SOA at baseline, Day 113 (Week 16), then every other dosing day (approximately every 168 days) or earlier if development of cirrhosis is suspected clinically, which may include development of varices, decompensating events or new thrombocytopenia and splenomegaly. Any increase from baseline to an APRI value >2.0 (must be confirmed on repeat) will trigger liver biopsy. For patients with baseline APRI >2.0 but who are eligible based on pre-dose biopsy, APRI will be calculated per SOA and a \geq 50% increase from baseline (must be confirmed on repeat) will trigger liver biopsy.

Investigator may elect to confirm an elevated APRI as a biomarker of cirrhosis with MRE if available PRIOR to proceeding to biopsy. If MRE is NOT consistent with cirrhosis then biopsy is not indicated and the patient may stay on study. Alternatively, the Investigator may elect to proceed directly from APRI to biopsy.

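### SAP addendum 6.3 prints APRI without a multiplier, so its values cannot be on the scale of the 2.0 level in protocol Appendix 2

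*SAP*

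**What the plan says.** Section 6.3 of the SAP addendum, under serum fibrosis markers, plans descriptive summaries of APRI at each open-label visit. It gives the definition as "APRI = ((AST(U/L))/(AST(upper limit of normal U/L)))/(Platelet Count(10^9/L", with no multiplying constant, and adds: "Derived changes from baseline and percent changes from baseline will be included". Section 4 leaves other matters to the main plan: "For other general definitions and data handling, refer to SAPv3.0".

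Protocol Appendix 2, in the stopping rule for progression to cirrhosis, says "APRI (using 40 U/L as ULN) will be calculated per SOA". The level it uses is in the next rule: "Any increase from baseline to an APRI value >2.0 (must be confirmed on repeat) will trigger liver biopsy". It then makes separate provision for a further group: "For patients with baseline APRI >2.0 but who are eligible based on pre-dose biopsy". For them a relative increase of at least 50% applies instead.

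Two entry limits in protocol section 7.3 bear on the values a patient can have at the start. Item 2 excludes "Platelet count $<150 \times 10^9/L$ at Screening (one retest permitted" and item 3 excludes "ALT and AST levels >250 U/L at Screening (one retest permitted".

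Neither document prints another APRI formula. Protocol section 9.3.8 lists ALT, AST and age as the inputs for APRI and FIB-4, without a formula and without naming platelets.

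**The concern.** Appendix 2 treats 2.0 as a value that a patient can reach on study, and that some eligible patients may exceed before the first dose. A definition of APRI used for the same patients in the same trial should be able to produce such values. The formula in SAP 6.3 cannot do so in practice.

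At stake is the readability of the open-label APRI tables. A programmer who follows section 6.3 exactly would report values and absolute changes on a scale that the protocol does not use. A reader could not set those values against 2.0, or against the APRI calculated on study for the same patients.

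**Working it through.** **Inputs**

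- Formula: APRI = (AST/ULN)/platelets, platelets in 10^9/L (SAP addendum 6.3)
- ULN for AST: 40 U/L (protocol Appendix 2)
- Level: 2.0 (protocol Appendix 2)
- Lowest platelet count at Screening: 150 x 10^9/L (protocol 7.3, item 2)
- AST 250 U/L (protocol 7.3, item 3), used as an illustration and not as a bound, because the item joins ALT and AST with 'and', so AST alone might exceed 250

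**Step 1. Can the printed formula give the protocol's 2.0?** Solving for AST:

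AST = 2.0 x ULN x platelets = 2.0 x 40 x 150 = 12,000 U/L.

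A higher platelet count needs more: at 250 x 10^9/L the figure is 2.0 x 40 x 250 = 20,000 U/L. So 2.0 is not reproduced at any credible entry value.

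**Step 2. What does the formula give?** At ULN 40 and platelets 150, for example 250/40/150 = 0.0417. The last column applies a multiplier of 100, which is an assumption.

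| AST (U/L) | As printed | 2.0 divided by printed value | With x 100 |
|---|---|---|---|
| 120 | 0.0200 | 100 | 2.00 |
| 250 | 0.0417 | 48 | 4.17 |
| 500 | 0.0833 | 24 | 8.33 |
| 1,000 | 0.1667 | 12 | 16.7 |

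**Step 3. Does another reading remove the gap?**

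- If item 3 excludes only patients with both enzymes above 250, AST may be higher at entry. AST 1,000 still falls short by a factor of 12.
- With a laboratory ULN of 30 or 50 U/L (assumed range), the AST needed is 2.0 x 30 x 150 = 9,000 or 2.0 x 50 x 150 = 15,000 U/L.
- If platelets fall on study to 50 x 10^9/L (assumed), the AST needed is 2.0 x 40 x 50 = 4,000 U/L.

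**Step 4. What multiplier would be needed?** At ULN 40 and platelets 150, the smallest multiplier that brings 2.0 within reach is 12,000/AST: 48, 24 and 12 for AST 250, 500 and 1,000. A multiplier of 100 puts 2.0 at AST 12,000/100 = 120 U/L, which fits Appendix 2's provision for eligible patients above 2.0 at baseline.

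**Step 5. Which outputs change?** Take AST rising from 60 to 90 U/L at platelets 200 and ULN 40.

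- As printed: 60/40/200 = 0.00750 and 90/40/200 = 0.01125, a change of 0.00375.
- With x 100: 0.750 and 1.125, a change of 0.375.
- Percent change: 50% in both cases.

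Values and absolute changes depend on the multiplier. Percent changes, and the 50% relative rule in Appendix 2, do not.

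**The case against.** The arithmetic is not in dispute. The case on the other side is about how sure one can be that the plan is wrong, and how much it matters.

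- **The factor may have been lost in text conversion.** The brackets balance and the FIB-4 formula just above reads complete, which makes a loss less likely. But a trailing factor would sit outside the last bracket, and losing it would leave the brackets balanced. This stands as a limit, and it is why the source file should be checked first.
- **SAPv3.0 may define APRI correctly.** That is possible. But the addendum prints its own formula for the open-label summaries, and its introduction says that analyses already described in SAPv3.0 are not repeated. The printed line is therefore the one a programmer would use. Whether the double-blind tables share it is unknown.
- **The affected tables do not use 2.0.** True. Section 6.3 plans no threshold or responder category, section 6.2 plans no separate efficacy analyses, and APRI is exploratory in protocol section 5.4. Appendix 2 does not refer to the SAP formula. This limits the severity; it does not make the formula right, because values and absolute changes are planned outputs.
- **The figure 100 is in neither document.** True. The mismatch stands without it. Only the 100-fold size and the exact form of the corrected equation depend on it.
- **The word 'cannot' is practical and not algebraic.** True. The printed formula would reach 2.0 with AST in the thousands.

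**Conclusion.** The point holds and is minor. On the documents' own figures, the printed formula needs AST 12,000 U/L to reach 2.0 at platelets 150 x 10^9/L and ULN 40 U/L. It gives 0.042 at AST 250 U/L, 48-fold below the level. Other readings of the entry criteria, the ULN or the platelet count narrow or widen the gap but do not close it.

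If the intended multiplier is 100 and the same ULN is used, both of which are assumptions, open-label APRI values and absolute changes would be 100-fold too small. Confidence is high that the text as available does not match Appendix 2. Whether the signed addendum contains the error depends on the source file.

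**What to change.** 1. Check the APRI multiplier in the source file of the addendum, in SAPv3.0, and in the calculation used on study under Appendix 2.
2. Correct section 6.3 to the Appendix 2 scale. If 100 is confirmed, write APRI = 100 x (AST/ULN)/platelets (10^9/L).
3. Check the derivation program. If SAPv3.0 prints the same expression, correct the double-blind derivation as well.

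While that line is open, it would help to state whether the ULN of 40 U/L or the laboratory's own range applies to these summaries. That is a separate, smaller clarification and does not cause the mismatch.

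The cost is one line of text and a program check. No new data are needed, and nothing in the Appendix 2 rule changes.
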